8. STUDY DEVICE AND TREATMENT PROCEDURE

The study device is described briefly below.

8.1 Description

The Myoscience iovera[°] device is a next generation device designed to temporarily reduce pain. The device consists of a reusable, portable Handpiece, along with single-patient use sterile Smart Tips (aka cryoprobes) and disposable nitrous oxide (N₂O) cartridges. The Smart Tip contains embedded software that manages procedure parameters and provides physician feedback throughout all states of device preparation, treatment and post-treatment via communication with the Handpiece. The Handpiece is battery powered and is stored and recharged via the Charging Dock.

The iovera[°] device produces the desired effect through initiation of a cooling cycle. Each cooling cycle is initiated by fully inserting the Smart Tip into the selected procedure site and activating the cryogen flow. A freezing zone forms around the end of the Smart tip affecting the adjacent tissue.

The cryogen is provided in a nitrous oxide cylinder attached to a custom filter, known as the Cartridge. To remove contaminants that may be present in the cylinder, a custom filter is added to the cylinder to filter the liquid nitrous oxide before it enters the Handpiece. This ensures optimal performance of the device.

A specially designed Smart Tip is included. The Smart Tip needles are made of stainless steel and have a closed-tip, fully enclosing the cryogen. As the cryogen gas travels through the length of the needle, an ice ball develops around the needle causing the surrounding tissue to be frozen. Operation instructions and further details on the device are provided in the *User Guide*.

Device training will be provided to the Investigator and study staff prior to the initiation of study enrollment.

[figure not shown]
8.2 Instructions for Use and Administration

Use of the iovera[°] device is described briefly herein. For details see the *User Guide* as provided by Myoscience, Inc.

The iovera[°] device is used on awake Subjects who are prepared with local anesthesia only. The treatment targets are the infrapatellar branch of the saphenous nerve (ISN) and the

[figure not shown]
anterior femoral cutaneous nerve (AFCN) shown in Figure 1. Training for the treatment procedure will be provided to the Investigator and study staff prior to the initiation of study enrollment.

Figure 1. Infrapatellar branch of the Saphenous Nerve and Anterior Femoral Cutaneous Nerve

Treatment will be performed unilaterally and will be guided by visualization and palpation of anatomical landmarks. Landmarks and treatment line will be marked on the skin as shown in Figure 2.

Figure 2 Treatment Lines (not to scale)

Note that the study Sponsor will provide the following supplies:

- iovera[°] devices, Smart Tips and cryogen cartridges
- Surgical pen or other marking tool
- Measuring tape
- Goniometers (2)

- Stop Watch
- Marking Ruler

The investigational site will provide the following:

- Injectable lidocaine (no epinephrine) used for local anesthesia
- Syringes for administration of local anesthesia
- Needles for administration of local anesthesia
- Gauze
- Alcohol wipes
- Wound dressing(s)

8.3 Contraindications

Use of iovera[°] is contraindicated in the following situations:

- Cryoglobulinemia
- Paroxysmal cold hemoglobinuria
- Cold urticaria
- Raynaud's disease
- Open and/or infected wounds in the target treatment area

Note: physician discretion should be exercised when patient presents with existing neuromuscular disease compromising the regeneration of peripheral nerves that may be involved in the treatment.

8.4 Risks

The iovera[°] device involves percutaneous access to subcutaneous tissue using a needle and use of dermal anesthesia. Passage of a needle into the skin, cooling of subcutaneous soft tissue and delivery of local anesthesia are known to be associated with the following risks:

- Bruising (ecchymosis)
- Swelling (edema)
- Inflammation and/or redness (erythema)
- Pain and/or tenderness along the treatment line
- Altered sensation (localized dysesthesia)

Proper use of the device as described in the *User Guide* can help reduce or prevent the following complications:

[figure not shown]
- Injury to the skin related to application of cold or heat
- Hyper- or hypo-pigmentation at the treatment site
- Skin dimpling at the treatment site
- Loss of motor function outside the target area

9. STUDY PROCEDURES

9.1 Overview

An Overview of the study visits is shown in **Figure 3**. Eligible Subjects are randomized to iovera[°] treatment or to the standard of care group. The standard of care group treatment consists of all of the standard pre-, peri- and post-operative protocols except that the iovera treatment is not provided. The primary endpoint is cumulative opioid consumption at 6 Weeks Post-TKA.

Figure 3. Overview of Study Visits

*Screening and Treatment can occur on the same day.

9.2 Recruitment

Potential study participants will be recruited from the clinics of the participating Investigator, as well as local advertising. Any study-related advertisements will be approved by the governing IRB prior to use.

9.3 Screening /Visit 1 (-30 to -1 days)

A patient who signs the informed consent document will be considered a study Subject. A Subject who withdraws from the study prior to randomization will not count toward the study's sample size. Potential participants will be screened for eligibility against **Table 1**.

Once the informed consent form is signed, the Subject is assigned a study number. The Subject number is comprised of the 2-digit site number followed by a consecutively assigned 3-digit Subject number that starts with 001. For example, the first screened Subject for site 01 will be assigned study number 01-001. The Subject number is the identification number used on CRFs and other study documents throughout the study. In the event a Subject withdraws from the study, their Subject number cannot be reassigned to any other Subject.

The Investigator, or designee, will document the Subject's medical history, demographic information, obtain vital signs and complete an assessment of the intended treatment areas and concomitant medications/concurrent procedures. Subjects will be asked to bring all prescription opioid bottles to all study follow-up visits. A pill count will be completed by the study coordinator, or designee.

Once a Subject has been determined to meet all inclusion and none of the exclusion criteria, the Subject will complete the following:

Assessments:

- NRS for Pain when standing from a seated position in target knee
- KOOS JR. (English version 1.0)

|

[REDACTED]

Physical Performance Measures in the following order:

- Timed Get Up and Go Test

Subjects may be complete Screening / Visit 1 and iovera[°] Treatment / Visit 2 on the same day.

9.4 Randomization

After meeting all of the inclusion and none of the exclusion criteria and prior to study treatment, Subjects will be randomized in a 1:1 manner to either:

- **iovera[°] Treatment:** Subject undergoes treatment with the study device using study supplied Smart Tip.
- **Standard of Care Treatment:** Subject does not undergo iovera[°] Treatment

The Investigator or designee will record the randomization assignment in the source documentation and CRF. Any Investigator who is discovered to tamper with randomization will be immediately terminated from the study.

9.5 iovera[°] Treatment/Visit 2 (5 Days +- 2 days prior to TKA)

Medical history will be reviewed as well as concomitant medications and procedures. Blood pressure and heart rate will be assessed. The Investigator, or designee, will reconfirm all eligibility criteria are met.

The iovera[°] device will be prepared by the trained Investigator (or Sponsor designee) according to the **User Guide**. If at any time the device does not perform as expected the Investigator (or designee) will follow procedures as outlined in the **User Guide**.

Prior to the initiation of the iovera[°] treatment, the Investigator, or designee, will mark the treatment lines on the knee to be treated as shown in Figure 2 located in section 8.2.

Then the skin along the treatment lines will be cleansed with alcohol. Lidocaine, no epinephrine, will be injected along the treatment lines superficially in order to achieve cutaneous anesthesia and to the bottom of the subcutaneous layer, atop the fascia, to temporarily block conduction of the infrapatellar branch of the saphenous nerve and the anterior femoral cutaneous nerve.

Once localized anesthesia of the treatment lines and the nerves is achieved, the Investigator, or designee, will complete the iovera[°] treatment along the treatment lines. Regardless of the length of treatment lines (width of patella or from lower pole of the patella down to tibial tubercle), adjacent insertions are placed along the treatment lines until the entire line has been treated so all Subjects receive the same treatment. Treatment is not to be modified or influenced by any Subject response to changes in knee pain. Representatives of Myoscience, Inc. may be present during the treatment. Photos of the treatment area may be taken.

Upon completion of treatment, the treatment areas will be cleansed and the skin will be left undressed. The Investigator or designee will assess the treatment areas for adverse events. A dressing may then be applied.

The Subject will be instructed to report any adverse events to the Investigator between and at the follow-up visits.

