The total number of outpatient Physical Therapy visits conducted between each study visit will also be obtained. Additional Data collected from Physical Therapy Visits will include:

- Pain while seated

Subjects will be asked to bring all prescription opioid bottles to all study follow-up visits. A pill count will be completed by the study coordinator, or designee, and opioid medication will be redisensed to subjects.

At the completion of this visit, the Subject will be exited from the study unless the Subject has any ongoing device-related or iovera^o treatment-related adverse events as described in section 10.8.

Table 2. Schedule of Assessments

Assessment	Visit 1 / Screening	Visit 2 / Iovera [®] Treatment	Visit 3 / DAY OF TKA (Day 0)	Visit 4 / 72 Hours Post-op	Visit 5 / 2 Weeks Post-op	Visit 6 / 6 Weeks Post-op	Visit 7 / 12 Weeks Post-op
Informed Consent	X						
Eligibility	X	X					
Medical history	X	X					
Concomitant medication assessment	X	X	X	X	X	X	X
Prior/Concurrent Therapy	X	X		X	X	X	X
Randomization*	X						
Study Treatment		X					
Physical Exam	X						
Vital signs	X	X					
Knee Circumference	X						
KOOS JR. Questionnaire	X			X	X	X	X
NRS for Pain	X			X	X	X	X
Subject Satisfaction Questions						X	X
Physical Performance Measures	X				X	X	X
Pain Medication Accountability				X	X	X	X
AE/SAE Assessment		X	X	X	X	X	X

* Randomization occurs after the subject has met eligibility criteria

Follow-up visits generally consist of the following:

- The Investigator or designee assesses the occurrence of health status changes and adverse events since last study visit;
- The Investigator or designee determines whether any changes in daily medications have occurred;
- The Investigator or designee performs drug accountability (pill counts) of post-operative outpatient opioid medication and re-dispenses unused opioid medications to subjects after use. The Investigator or designee records other over-the-counter concurrent pain medication use and pain relief therapies used per subject report;
- The Subject completes a KOOS JR. questionnaire, [REDACTED] Satisfaction questions (Visit 6 and 7 only), and reports NRS for Pain when standing from a seated position;
- The Investigator or designee performs Physical Performance Measures ([REDACTED] Get Up and Go Test).

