11. ADVERSE EVENTS

The study Investigator and Coordinator will evaluate, characterize and record in the CRF all adverse events (AEs) occurring in all subjects from the initiation of study treatment to study exit (or premature withdrawal). Device or procedure related AEs will be followed until resolution. AEs may be reported spontaneously by the subject or detected by the Investigator or coordinator. AEs should be evaluated for diagnoses not just symptoms (i.e., “angina”, not “chest pain”).

AEs may be either spontaneously reported or elicited during questioning and examination of a subject. All AEs must be completely recorded within the Subject's source documentation. All AEs will be evaluated by the Investigator for relationship to the iovera[°] device and to the treatment.

In addition to verbatim terms, the Sponsor will categorize all AEs using MedDRA preferred terms and system organ classes (SOC). Analysis will report both verbatim and MedDRA terms.

Adverse events¹ (AEs) will be assessed continuously from the initiation of study treatment through study exit. Per ISO14155:2011, an AE is any untoward medical occurrence, unintended disease or injury, or untoward clinical signs in subjects, users or other persons, whether or not related to the investigational medical device. An AE can arise from any use of the device (e.g., off-label use, use in combination with any drug) and from any route of administration.

Timely and complete reporting of all AEs assists the Sponsor in identifying any untoward medical occurrence, thereby allowing:

- 1) protection of the safety of study subjects;
- 2) a greater understanding of the overall safety profile of the device;
- 3) recognition of device-related ill effects;
- 4) appropriate modification of study protocols;
- 5) improvements in study design or procedures; and
- 6) adherence to worldwide regulatory requirements.

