## **9.0 SAFETY ANALYSES**

All adverse event analyses will be performed on the Safety Population.

The summary of AEs will be limited to treatment emergent AEs. For AEs with a missing start date, the AE will be considered treatment emergent unless there is additional information indicating that the AE started prior to study treatment.

Adverse events (AEs) will be coded using the Medical Dictionary for Regulatory Activities (MedDRA). Treatment-emergent AEs (TEAEs) are defined as any adverse event with onset on or after study treatment begins or any adverse event already present at baseline that worsens in severity. For AEs with missing start dates, the AE will be considered treatment-emergent unless there is additional information indicating that the AE started prior to study treatment. Only treatment emergent AEs will be summarized.

The number and percentage of subjects with at least one TEAE, at least one iovera procedure-related TEAE, at least one iovera device-related TEAE, at least one opioid use related TEAE, at least one serious TEAE, and at least one TEAE leading to study withdrawal will be presented by treatment group. AEs that are definitely, probably, or possibly related, or for which the relationship is missing, will be considered related.

The number and percentage of subjects having a TEAE in each System Organ Class (SOC) and having each individual type of adverse event (Preferred Term) will be presented. TEAEs will also be summarized at the event level by SOC/Preferred Term and severity. This will be done for all TEAEs, iovera procedure related TEAEs, iovera device related TEAEs, and opioid use related TEAEs.

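### The protocol writes the instruction to report adverse events between visits only into the iovera procedure, with no equivalent for standard-of-care subjects

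*Protocol*

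**What the plan says.** Protocol 9.5 covers Visit 2. It ends with cleansing of the treated skin, a check of the treatment areas for adverse events, an optional dressing, and then this sentence: "The Subject will be instructed to report any adverse events to the Investigator between and at the follow-up visits".

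Protocol 9.4 defines the control arm by the absence of that procedure: "Subject does not undergo iovera[°] Treatment". Section 9.1 says controls have all the standard care around the operation "except that the iovera treatment is not provided".

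Protocol 11 asks the site to "record in the CRF all adverse events (AEs) occurring in all subjects from the initiation of study treatment to study exit" and names two ways an event can come to light: "AEs may be either spontaneously reported or elicited during questioning and examination of a subject". For follow-up visits, section 9.7 adds: "The Investigator or designee assesses the occurrence of health status changes and adverse events since last study visit".

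SAP 3.3 states that the study is unblinded. SAP 9.0 tabulates subject counts by arm, from any treatment-emergent event through "at least one TEAE leading to study withdrawal will be presented by treatment group", and includes opioid-related events.

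**The concern.** Section 11 counts on subjects volunteering events as well as on staff asking: "AEs may be reported spontaneously by the subject or detected by the Investigator or coordinator". A subject who has been told to report between visits is more likely to do so than one who has not. If that prompt is given in one arm only, the arms may differ in how many events are volunteered, and how soon, for reasons unrelated to the device.

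Two things are at stake. First, SAP Tables 8.1 to 8.3, 9.5 and 9.6 set iovera beside standard of care. Extra prompting in the iovera arm would push its counts up and work against the device, including for opioid-related events in a trial about reducing opioid use. Second, the 24-hour report of a serious event to the sponsor (Protocol 11.2) runs from the site becoming aware of it. A later report from an unprompted subject would start that clock later.

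**Working it through.** The plan states no figure on this point, so the check is mainly a comparison of text.

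**1. Where the instruction is written.**

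| Protocol section | Arms it applies to | Instruction to report between visits? |
|---|---|---|
| 9.3 Screening | Both | No. Subjects are asked here to bring opioid bottles to follow-up visits |
| 9.4 Randomization | Both | No |
| 9.5 Visit 2, closing text | Follows the iovera procedure | Yes |
| 9.6 Surgery and discharge | Both | No |
| 9.7 Follow-up | Both | No. Events are reported or assessed at each contact |
| 11 Adverse events | Both | No. Spontaneous reports are named as a route, without saying who is told to make them |

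The request about opioid bottles shows that the protocol can place a subject instruction before randomization, where both arms receive it.

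**2. What is collected in the same way in both arms.** In-patient events come from hospital records (9.6). Subjects report events at the 72-hour call, and events are assessed at Visits 5, 6 and 7 (9.7). Each follow-up visit looks back to the previous one. The adverse event row of Protocol Table 2 is not split by arm.

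**3. Intervals that rest on recall when nothing is volunteered.** Using nominal visit days:
- 72 hours to Week 2: 14 − 3 = 11 days
- Week 2 to Week 6: 42 − 14 = 28 days
- Week 6 to Week 12: 84 − 42 = 42 days

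**4. Which outputs could be affected.** Tables 8.1 to 8.3, 9.5 and 9.6 show both arms. Tables 9.1 to 9.4 (procedure- and device-related events) have no control column, and the corresponding rows of Table 8.1 carry a dash for controls. Those outputs are unaffected as between-arm comparisons.

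**5. Illustration under assumptions.** The documents give neither an event rate nor a capture rate. Assume that a proportion p of subjects in each arm truly has an event, that capture is complete with iovera, and that a fraction c is captured in controls. The spurious difference is p × (1 − c), and in 60 subjects it amounts to 60 × p × (1 − c).

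| p | c | Difference | Subjects of 60 |
|---|---|---|---|
| Any | 1.00 | 0 points | 0 |
| 0.10 | 0.95 | 0.10 × 0.05 = 0.5 points | 0.3 |
| 0.30 | 0.90 | 0.30 × 0.10 = 3 points | 1.8 |
| 0.50 | 0.80 | 0.50 × 0.20 = 10 points | 6 |

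Every input here is assumed. The range shows how the result depends on c and is no evidence that c is below 1. The look-back makes values near 1 plausible.

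**The case against.** The strongest reply is that collection rules do not differ by arm. Events are recorded for all subjects, and staff ask about the whole interval at each follow-up contact. An event not volunteered between visits should surface at the next one. The prompt is also weak: it is given once, 3 to 7 days before surgery (5 ± 2 days), and is not repeated for iovera subjects either. The safety summaries are descriptive, with no between-arm test. All of this stands, and it is why the effect is probably small.

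A reader might go further and infer that control subjects never receive the instruction. The documents do not support that. It would be drawn only from where the sentence sits. Nothing says whether controls attend Visit 2. Section 9.5 opens with steps not specific to the device, and the Visit 2 column of Table 2 is not split by arm. The consent form, where such an instruction could appear, is not in the text available.

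A reader might also infer that the by-arm rates are biased by some definite amount, or that serious events in controls will go unreported until the next visit. Neither is shown. Any percentage comes from assumed capture rates. Events that meet the seriousness criteria of section 11.2 may well reach the site by other means, so delay is only a possibility.

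What the reply does not remove is the text itself: one of the two detection routes is prompted by the protocol in one arm and left unprompted in the other, with no blinding.

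**Conclusion.** The point holds in a limited form. As written, the protocol directs the between-visit reporting instruction only at the end of the iovera procedure, which exposes the by-arm summaries of all treatment-emergent and opioid-related events to some unequal prompting. Any effect would mainly concern mild or transient events, which are the most easily forgotten over gaps of 28 and 42 days, and the timeliness of reports. Its direction, if present, would be against iovera. Its size cannot be determined from the documents. Severity is minor.

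The conclusion rests on reading the protocol literally and on no equivalent instruction being given elsewhere. If controls are already told the same thing in practice or in the consent form, the change simply records it.

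**What to change.** Move the sentence out of section 9.5 and into section 9.4, so that it is given at randomization to every subject in both arms. Repeat it at discharge in section 9.6, using identical wording for every randomized subject. Keep only the treatment-area check in section 9.5. Possible text: *Every randomized subject, in either arm, is told to report any adverse event to the Investigator when it occurs, as well as at each follow-up contact.*

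The cost is one moved sentence and one repetition, with the IRB approval that section 14.4 requires for any protocol revision. No visit, staff or procedure is added, and the SAP need not change.

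A separate gap is left open by this edit. Adverse event recording (Protocol 11) and the treatment-emergent definition (SAP 9.0) both start at study treatment, and no start is stated for controls. That needs its own clarification.

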9.6 Visit 3 / Total Knee Arthroplasty (Day 0)

The Investigator or Designee will confirm their ability to safely perform TKA within the following protocol requirements. All surgical and in-patient data, safety information including adverse event assessments, will be collected retrospectively from hospitalization records:

- Pre-operative History & Physical Exam, including assessment of the target knee, must be documented in the medical record and included as study data.
- Surgery and Implant - Medial parapatellar surgical approach; cruciate-retaining or posterior-stabilized TKA; all surfaces replaced.
- Pre-emptive analgesia – medications administered prior to TKA, orally, intravenously, or otherwise, for the purpose of pain management before, during, or after surgery, are to be recorded in the medical record and included as study data.
- Procedural anesthesia – during Arthroplasty this will be limited to spinal anesthesia, the formulation, or “cocktail,” of medications used are to be recorded in the medical record and included as study data.
- Local Infiltration Analgesia – The control group (standard of care) may utilize local infiltration analgesia (including periarticular and posterior capsule infiltration). The use of periarticular local infiltration analgesia (eg. Exparel) is not permitted to be used as part of this protocol in the treatment (iovera) group. However, for the treatment group, local infiltration analgesia may be used in the posterior capsule as the iovera treatment does not affect this region of the knee. The medications used in both groups are to be recorded in the medical record and included as study data.
- Regional nerve block for post-operative analgesia – single shot Adductor Canal Block required, the formulation, or “cocktail,” of medications used are to be recorded in the medical record and included as study data.
- Post-operative analgesia will be prescribed as detailed below. All opioid or other pain medications used are to be recorded in the medical record and included as study data.
 - Oxycodone, 5mg, q4h/PRN, N=40
 - Tramadol, 50mg q6, N=40
 - Tylenol, 100mg, TID, N=40
 - Neurontin, 100mg, TID, N=40
 - Meloxicam, 15mg, OD, N=15
- Post-operative discharge criteria: Ability to tolerate fluids, ambulate with physical therapist for first ambulation, Void >200cc, Pain under control.
- Other data to be collected retrospectively from hospitalization medical records may include: [REDACTED] pain scores collected during physical therapy and adverse events, including Opioid-related adverse events.

Outpatient analgesia – The subject will be required to bring all of their unused prescription narcotic medications dispensed during study participation to all study follow-up visits for pill count. A pill count/ accountability will be completed by the study coordinator, or designee. Any other over-the-counter analgesic medications or other pain relief therapies

used (per patient report) will also be recorded by the study coordinator, or designee, at each follow-up visit.

